BAT and cardiovascular function. Recent studies have investigated the endocrine role of BAT to influence cardiovascular function. UCP1^{-/-} knockout mice had greater cell death, greater adverse remodeling, and worse survival in catecholamine-induced cardiomyopathy (38). These detrimental effects in UCP1^{-/-} knockout mice were prevented with transplantation of BAT from wild-type mice, suggesting that thermogenically active BAT has a cardioprotective effect. Additionally, BAT transplantation increases glucose uptake to the heart (36). Taken together, these studies indicated that BAT can influence heart function.

BAT as an endocrine organ. BAT functions as a secretory organ, releasing various secreted factors that act on other tissues and organs (2, 14, 36, 40). Several BAT-derived molecules, called “batokines” have been identified to function in an autocrine, paracrine, and endocrine manner (40). Previous studies have demonstrated that increasing the amount of BAT through a transplantation model improved whole-body metabolic health and increased insulin-stimulated glucose uptake in the heart and WAT (14, 36). Recent work has identified a batokine, the lipid 12,13-diHOME, to be increased in circulation in response to various stimuli in both rodents and humans and increases fatty acid uptake in BAT and skeletal muscle (25, 39). In line with a reduction in BAT, 12,13-diHOME is decreased in older adults in comparison to young counterparts (35). These studies suggest the inability of BAT to secrete batokines with aging may impair whole-body metabolism and cardiovascular function in older adults.

Study Objectives

Primary Objective

To define the role of BAT and 12,13-diHOME in the age-induced impairments in metabolism and cardiac function, and determine if increasing BAT mass or its endocrine function is a viable therapeutic strategy to improve metabolic and cardiovascular function in the elderly.

Study Design

Research Design

The proposed clinical study is a single site prospective, two group, controlled exercise training study of older athletes (OA) (n=15 completers) and older sedentary (OA) (n=15 completers) consisting of three distinct but connected phases:

Phase I: Pre-Intervention, Screening and Baseline testing

Phase II: Intervention, Exercise Training

Phase III: Post-Intervention, Follow-Up testing

A series of physiologic and clinical/health outcomes will be assessed before and after the exercise intervention period:

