1. Morning resting fasted variables: blood pressure; blood glucose and lipids
2. Physical Examination, Resting ECG, Urine collection
3. Cardiorespiratory fitness (VO₂peak) determined via a graded cycle ergometry test.
4. Physical function: The Short physical performance battery (SPPB) will be used to measure lower extremity performance as a secondary outcome.
5. Body composition by DEXA scan - bone mineral density, total and partitioned lean mass, estimated visceral fat.
6. Muscle strength and power: Quadriceps muscle performance testing (maximal strength and power) will be performed using a Biodex dynamometer.
7. Hyperinsulinemic euglycemic glucose clamp to assess whole body insulin sensitivity.
8. Echocardiograph measurements to assess cardiac function.
9. MR Imaging for BAT Mass

Participants in the OS group will enter a progressive 8-week supervised aerobic and resistance training program at the exercise training facility at the TRI. Blood will be collected before and after the intervention to assess circulating Batokines. A complete Schedule of Activities (SOA) can be found in the Appendix.

The expected duration for a participant in this study is approximately 120 days.

Males and females in the age ranges 65-90 years will be recruited from AdventHealth's electronic medical record (EMR), senior centers, television, radio and social media advertisements, mass mailing lists from the Orlando, FL catchment area, and by contacting potential participants on the AdventHealth TRI's participant database.

Study Site(s)/Location(s) and Number of Participants

AdventHealth Orlando site locations: Translational Research Institute, [name].

Estimated number of participants at AdventHealth Orlando site (including screenings): 36

Estimated number of participants at external sites: 0

Total number of all sites: 1

Estimated number of participants at all sites combined (including screenings): 36

Multi-Site Research Logistics/Communication Plan

N/A

Research Conducted in a Foreign Country

N/A

Community-Based Participatory Research

N/A

Participants Selection

Vulnerable Populations (if applicable)

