Participants Recruitment and Screening

Males and females in the age ranges 65-90 years will be recruited from AdventHealth EMR, senior centers, television, radio, social media advertisements, text messaging, emailing, newsletters, and mass mailing lists from the Orlando, FL catchment area, and by contacting potential participants on the AdventHealth TRI's participant database.

Potential participants will be medically screened to determine good health and without any contraindication to exercise. Approximately equal numbers of men and women will be recruited. Neither race nor ethnicity will be exclusions.

We will recruit volunteers through public advertisement by placing advertisements in community newspapers and radio, as well as on social media. Individuals who respond to

the ads will be contacted by telephone for preliminary screening and will be given an opportunity to ask initial questions and be provided additional description of the study. Potential volunteers who seem to meet criteria will be scheduled for an outpatient examination at AdventHealth TRI. Informed, written consent will be obtained at the screening visit.

We anticipate ~400 phone screens to successfully enroll and complete 18 participants per group (anticipating 15 completers per group).

Consent Process

We attest that all study staff delegated the authority to obtain informed consent will follow “Investigator Guidance: Informed Consent (HRP-802)”, as well as “Investigator Guidance: Documentation of Informed Consent (HRP-803)”.

Non-English Speaking Participants

We will not be enrolling Non-English speaking participants due to the complexity of the visits, number of visits and length of the study. The participant population will be English speaking.

Participants who are not yet adults (infants, children, teenagers)

We are not enrolling participants who are not yet adults.

Cognitively Impaired Adults

We will not enroll cognitively impaired adults.

Adults Unable to Consent

We will not enroll adults who are unable to provide consent.

Documentation of Informed Consent Process

Documentation of the informed consent process is required to establish that the participant was accurately and adequately informed and that no study-related procedures were initiated prior to obtaining informed consent. A research team member will note in the source documentation the consent process, date consent was obtained, and that consent was obtained prior to initiating any research procedures.

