Waist Circumference Measurements which are a surrogate measure of abdominal fat will be conducted during screening. The Gulick II tape measure will be used for accuracy in obtaining duplicate waist measurements. All circumferences will be measured in centimeters directly on the skin.

Hand-Grip Strength Test. All participants will perform a hand grip test that will be conducted three times with 1 minute of rest between each repetition using the dominant hand of each participant. The greatest grip strength and the average of the three tests will be recorded.

Lower extremity performance battery. The Short Physical Performance Battery (SPPB) is a brief performance-based test that will be used to measure lower extremity performance. The SPPB consists of three tasks: five repeated timed chair stands, timed standing balance (with feet in parallel, semi-tandem, and tandem positions), and a 4-meter walk to determine usual gait speed.

Step Test: Each participant will be asked to complete a timed step test.

Covid Testing: Participant must have a negative covid test 1 week prior to the next visit. Covid testing may take place on a separate visit when SV1 is not within 1 week of V1.

Screening tests may be repeated if the Investigator deems necessary.

Visit 1

Approximate visit time: ~ 3 hours

Review of Adverse Events, Concomitant Medications

Vital Signs

Body Weight

3-Day Food Diary: Participants will be given a food diary and asked to record what foods and drinks they eat over a 3-day period. Participants will return the completed diary on visit 2.

Fasting blood draw to collect EDTA plasma. Circulating lipids related to BAT activity and mass will be measured in plasma samples. Total blood volume will be 10 mls. Safety labs may be repeated per Investigator discretion, if needed.

MR Imaging for BAT Mass. Brown adipose tissue will be differentiated from white adipose tissue using fat fraction and T2* relaxation time maps generated from a commercially available modified 6-point Dixon (mDixon) water-fat separation method. MRI scans will be performed on a Philips 3T using axial, coronal, and sagittal slice orientations to provide anatomical reference scans in the neck and body area. Quantitative mDixon scans will be used for calculating proton density fat fraction (PDFF) maps. The participant may be removed from the magnet and repositioned during the exam in order to determine the same day variability of this method.

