Exercise compliance will be monitored for exercise training 4 days per week (minimum of 32 total sessions). Aerobic training will be 30 minutes of brisk walking, jogging, cycle ergometry. Walking will be the primary mode of aerobic exercise given its widespread popularity and ease of administration across a broad segment of the older adult population. Walking will be at a moderate intensity and determined based on Heart Rate (50-70% of Maximal HR from most recent VO₂max) and rating of perceived exertion using Borg's scale (ranges from 6 to 20). Other forms of endurance activity (e.g., stationary cycling) will be utilized on a limited basis when regular walking is contraindicated either medically or behaviorally. This is the exercise regimen that has demonstrated substantial increases in muscle size and strength in elderly people. See "Appendix: Schedule of Activities" for a table description of the procedures that will be performed during PHASE II.

PHASE III – POST-INTERVENTION TESTING

Following the exercise training intervention, participants in the OS group will participate in post-intervention testing. The testing procedures are a subset of those performed during the pre-intervention testing period (PHASE I). A detailed description of the procedures can be found above. The testing procedures will be taken over a 2-week period following the exercise intervention. See "Appendix: Schedule of Activities" for a table description of the procedures that will be performed during PHASE III.

Study Duration

Estimated start date for enrollment is Sept 30, 2019. Active recruitment and testing will continue until the end of the funding period or until 15 participants per group have been recruited. The study is funded by the National Institute of Aging until 01/31/2024.

Materials of Human Origin: Collection, Preparation, Handling and Shipping

Materials of human origin will be collected in the manner described in the specific study visits section of this protocol.

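### The recruitment stop rule triggers at 15 per group recruited, while the design needs 15 completers from 18 enrolled; 'recruited', 'enrolled' and the total of 36 need one definition

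*Combined protocol and SAP*

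**What the plan says.** All references are to the combined protocol and SAP.

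- **Study Duration** gives the stop rule: "Active recruitment and testing will continue until the end of the funding period or until 15 participants per group have been recruited". It puts the end of funding at 01/31/2024.
- **Research Design** sets the size in completers: "older athletes (OA) (n=15 completers", and the same number for the sedentary group. It also says: "The expected duration for a participant in this study is approximately 120 days".
- **Participants Recruitment and Screening** plans to "enroll and complete 18 participants per group (anticipating 15 completers per group". It adds: "Informed, written consent will be obtained at the screening visit".
- **Study Site(s)/Location(s) and Number of Participants** has: "Estimated number of participants at AdventHealth Orlando site (including screenings): 36".
- **Study Outcome Measures** wants BAT imaging and lipokines from 15 in each group. **Sample Size Determination** rests its power statement on 15 per group, without a formal calculation.
- **Statistical Analysis Plan** compares the groups at baseline by t-test and analyses the training effect in the OS group by repeated measures ANOVA.
- **Phase III** limits follow-up testing to one group: "participants in the OS group will participate in post-intervention testing".

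**The concern.** The same study size is expressed in three units: recruited (15), completers (15) and enrolled (18). A rule that stops at 15 recruited cannot also bring in 18 per group. The recruitment sentence adds to the confusion, because it speaks of completing 18 and of expecting 15 completers.

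The total has a related problem. Consent is taken at the screening visit, so a person who fails screening has already consented. A count of 36 that includes screenings cannot also be 18 enrolled in each of two groups unless nobody fails.

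The other branch of the rule ends recruitment and testing together when funding ends. Nothing says when the last OS participant must enter in order to finish.

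At stake is whether the OS pre/post analysis reaches its stated 15, and whether staff and the IRB are working to the same count.

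**Working it through.** **1. Reproduce the plan's figures.** The documents state no dropout rate. The recruitment section implies retention r = 15/18 = 0.833, a loss of 16.7%. Then 15/0.833 = 18 per group and 2 × 18 = 36. The sums agree. Because r is back-calculated from the same two numbers, this checks consistency only and does not support the rate.

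**2. Literal stop rule: 15 enrolled in OS.** Expected completers = 15r. The chance that all 15 complete is r^15. For comparison, the last column is the binomial chance of at least 15 completers from 18 enrolled. Participants are taken as independent with one common rate.

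| Retention r | Expected completers of 15 | P(all 15 complete) | P(at least 15 of 18) |
|---|---|---|---|
| 80% (assumed) | 12.0 | 3.5% | 50% |
| 15/18 (implied) | 12.5 | 6.5% | 65% |
| 90% (assumed) | 13.5 | 21% | 90% |
| 95% (assumed) | 14.25 | 46% | 99% |

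The 36 can also be read as 30 recruited plus 6 screen failures (30 + 6 = 36). The 18-to-15 gap is then all screen failure, the documents imply no dropout, and the expected number is 15.

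**3. Effect on precision (illustration only).** For a paired 95% interval, the half-width in SDs of the change is t(n−1)/√n: 0.554 at n = 15, 0.604 at n = 13 and 0.635 at n = 12. The ratios to n = 15 are 1.09 and 1.15, so the interval is 9 to 15% wider.

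**4. Which analysis is exposed.** BAT imaging for the group comparison is done at Visit 1: "MR Imaging for BAT Mass. Brown adipose tissue will be differentiated from white adipose tissue using fat fraction". The t-test is on baseline data. Only OS has eight weeks of training and follow-up testing, so dropout during training removes OS follow-up data.

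**5. The total of 36.** If 36 is the consented count and a fraction s fails screening, 36(1 − s) are enrolled. For assumed s of 10, 20 and 30% that is 32.4, 28.8 and 25.2, or 16.2, 14.4 and 12.6 per group. To enrol 36, the consented count would need to be 36/(1 − s), rounded up: 40, 45 and 52.

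**6. The funding branch.** In the Schedule of Activities, Visit 1 is at day −26 and the last visit at day 71: 71 + 26 = 97 days. 31 January 2024 minus 97 days is 26 October 2023. Counting the full 120 days from entry gives 3 October 2023. The current version is dated August 2023, so either date is close.

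**The case against.** The strongest defence is that recruited loosely means completed. The sentence governs recruitment and testing together, and testing cannot stop the moment the fifteenth person joins. Research Design, the recruitment section and the outcome section all point to 15 people with data. On that reading only the word is wrong. This is plausible, but the text does not say it, and staff applying the sentence as written would stop early.

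The defence is right to limit the consequences, and three stronger readings should be set aside.

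- *The main comparison loses power.* A reader might infer this from 12.5 completers per group. The documents do not support it: the power statement concerns BAT mass between active and sedentary groups, measured before training, and withdrawn participants' data may be used. No power claim is made for the OS pre/post analysis, so 12 or 13 crosses no stated threshold. The SAP also foresees repeated-measures modelling that allows for missing observations.
- *Nobody entering OS after 3 October 2023 could finish.* The 120 days are approximate, and the 28 days between screening and Visit 1 are an upper limit. A promptly scheduled participant with Visit 1 by about 26 October would finish on the nominal schedule.
- *The sums are wrong.* They are not: 2 × 18 = 36, and 15 of 18 is coherent. The units conflict.

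It also stands that retention is never stated and that the range runs to no shortfall at all.

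**Conclusion.** The stop rule is inconsistent with the plan's own size and should be reworded. That conclusion needs no assumption: 15 recruited and 18 enrolled cannot both be the end of recruitment, and recruited is undefined.

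The size of the harm is conditional on three things: the literal reading, this trigger binding before funding ends, and a retention rate. Given those, OS would be expected to have about 12.5 completers in place of 15 at the implied 15/18, with a range of 12.0 to 14.25 at assumed retention of 80 to 95%, and 15 if the gap is all screen failure. The effect is mainly on the OS pre/post analysis.

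The label on the 36 is a second inconsistency: it leaves no room for consented screen failures if 18 per group are to be enrolled. The funding branch is a third gap: on the nominal schedule, an OS participant with Visit 1 after about 26 October 2023 would not finish by 01/31/2024.

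**What to change.** 1. **Define enrolled** once: consented, found eligible, and having started Visit 1. Accelerometry, which helps verify group membership, is uploaded only at Visit 2 or Visit 3, so also say how someone who fails that check is counted.
2. **Study Duration**, replace the stop rule with: *Recruitment will continue until 15 participants per group have completed all visits scheduled for their group, or 18 per group have been enrolled, or the last entry date that allows an OS participant to finish within the funding period has passed, whichever is first. Testing of those already enrolled continues to their last scheduled visit.* State the last entry date.
3. **Participants Recruitment and Screening**: delete *and complete*, so that 18 is the enrolled number and 15 the completers expected.
4. **Number of Participants**: state that 36 is the enrolled count and give consented screen failures separately.

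The cost is a wording amendment and possibly a revised consented count with the IRB. Nobody is enrolled beyond the 18 per group already planned. The cap does not guarantee 15 completers: at 15/18 retention the chance of fewer than 15 is 1 − 0.648, about 35% per group (50% at 80% retention, 10% at 90%).

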DEXA: Dual-energy X-ray absorptiometry

DO: Doctor of Osteopathic Medicine

DVT: Deep Vein Thrombosis

ECG: Electrocardiogram

EMR: Electronic Medical Record

eGFR: estimated Glomerular Filtration Rate

FDA: Food and Drug Administration

HbA1c: Hemoglobin A1c

HDL: High-Density Lipoprotein

HIPAA: Health Insurance Portability and Accountability Act

HIV: Huma Immunodeficiency Virus

IRB: Institutional Review Board

LDL: Low-Density Lipoprotein

MD: Medical Doctor

MI: Medical Investigator

MMSE: Mini Mental State Examination

MRI: Magnetic Resonance Imaging

NP: Nurse Practitioner

OS: Old Sedentary

PA: Physician Assistant

PASE: Physical Activity Scale for the Elderly

PC: Personal Computer

PI: Principal Investigator

RER: Respiratory Exchange Ratio

RM: Repetition Maximum

SOP: Standard Operating Procedure

SPPB: Short Physical Performance Battery

TRI: Translational Research Institute

TSH: Thyroid Stimulation Hormone

UF: University of Florida

VLDL: Very Low-Density Lipoprotein

VO₂: Volume of Oxygen Consumed

WI: Working Instruction

YA: Young Active

Current Version Date: 11& the Aug2023

IRBNet #: 1456947

Page 4 of 32

Introduction

This document is a protocol for a human research study. This study is to be conducted in accordance with applicable Federal regulations and institutional research policies and procedures.

The US population is rapidly aging. It is projected by 2030, more than 20% of the population will be over 65 years of age (An Aging Nation: The Older Population in the United States. *Current Population Reports (US Census Bureau)*, 1-28 (2014)). Aging per se is the strongest risk factor for a multitude of diseases including both metabolic and cardiovascular disease. Increased age is also associated with a reduction on physical activity levels and exercise intolerance, resulting in decreased cardiorespiratory fitness (VO₂max). Many studies have shown that VO₂max strongly correlates to all-cause mortality (21). The effects of aging on the body include a loss of functional independence, a decrease in the quality of life, and an increased risk of mortality. The increase in the aged population has elevated the significance of elucidating potential therapeutic treatments.

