Physical inactivity and aging. Together, the collective effect of aging on metabolism, the cardiovascular system, and other organ systems concomitant with a reduction on physical activity levels leads to exercise intolerance. This inactivity decreases VO₂max, a leading risk factor in cardiovascular disease and all-cause mortality (21). This decrease in physical activity can result in a loss of functional independence and a decrease in quality of life.

Brown adipose tissue (BAT) and aging. BAT is a thermogenic tissue that produces energy as heat. It is characterized by a multilocular appearance, increased mitochondria, and increased expression of uncoupling protein-1 (UCP1) (30). Modulation of BAT metabolism influences whole body energy balance, and increased BAT activity counteracts obesity and diabetes (2, 7, 11, 13, 14, 24, 30, 36, 39). BAT is influenced by cold exposure through increased sympathetic activity (20, 28), various secreted factors (20, 25, 28), or exercise (4, 15-17, 22, 23, 27, 29, 34, 37, 41-45, 47). BAT mass and activity are decreased in humans and mice with aging (7, 12, 31-33). The decrease in BAT with age is due to blunted sympathetic activity (32, 33), altered endocrine control (32), and the loss of brown adipocyte regenerative capacity due to dysfunctional stem cells (32,

33). This decreased BAT activity is manifested in a diminished response to cold temperatures (i.e., reduced heat generation via non-shivering thermogenesis) (26, 31). There is also an inverse relationship of BAT to body mass index and visceral fat mass (7, 31). These data suggest that the loss of BAT contributes to the metabolic dysfunction with aging.

BAT and metabolism. Previous studies have demonstrated that increasing the amount of BAT in rodents using a transplantation model improved whole-body and metabolic health and increase insulin-stimulated glucose uptake (14, 36). BAT transplantation reduced body weight and adiposity and improved whole-body glucose metabolism. BAT transplantation increases glucose metabolism specifically in the heart, white adipose tissue (WAT), and the endogenous BAT (36).

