AdventHealth Orlando Employees: Recruitment efforts will follow AdventHealth Orlando recruitment SOPs for research. AdventHealth Orlando Employees will not be individually targeted nor excluded from study participation based on employment. AdventHealth Orlando employees who engage the AdventHealth TRI asking to participate in the study will be processed per standard consent procedures for participants. In addition, during the consent process, the study staff will review standard consent language stating that an employee's participation or lack of participation in the study will not affect their employment status or relationship with AdventHealth Orlando.

Inclusion Criteria

1. Males and Females between the ages of 65 to 90 years of age.
2. BMI $\leq 35\text{kg/m}^2$, inclusive at time of screening.
3. Stable weight (No gain/loss of ≥ 10 lbs within 6 months prior to screening).
4. Non-smokers as defined by not smoking any tobacco or using nicotine-containing products and not using vape pens or vaporizers within 3 months prior to screening.
5. Participant must have renal function with an estimated glomerular filtration rate (eGFR) $> 45 \text{ ml/min}/1.73\text{m}^2$ determined at screening.
6. Triglyceride level is $< 350 \text{ mg/dl}$ and LDL cholesterol is $\leq 150 \text{ mg/dl}$ at screening.
7. States willingness to follow protocol as described, including the prescribed exercise level and completing any forms needed throughout the study.
8. Voluntarily signed and dated an informed consent form, approved by an Institutional Review Board/Independent Ethics Committee, and provided Health Insurance Portability and Accountability Act authorization (HIPAA) or other privacy authorization prior to any participation in study.

Group Specific Inclusion Criteria:

9. Older Athletes (OA) Only: Endurance trained athletes, defined as exercising (running, cycling, swimming) $>3\text{days/wk}$ for >6 months without layoff. This will be verified by self-report and triaxial accelerometry.
10. Older Sedentary (OS) Only: Defined as $<1\text{day/wk}$ of structured exercise and determined by self-report and triaxial accelerometry.

Exclusion Criteria

1. History of type 1 or type 2 diabetes per self-report at screening visit 1.
2. Actively pursuing weight loss and/or lifestyle changes at time of screening.

3. Untreated or poorly controlled hypertension (SBP > 150, DBP > 95).
4. Mini Mental State Exam (MMSE) <21.

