The primary purpose of this protocol is to understand the role of physical activity on BAT mass and circulating batokines, and how these variables relate to cardiac and physical function in older adults. A formal sample size calculation was not performed. Rather, we referred to published studies with similar experimental designs (determination of BAT mass by PET scan) as a guide for sample size determination. From the published literature we determine that an n=15 per group (active and sedentary) will provide sufficient statistical power to detect differences in BAT mass.

Statistical Analysis Plan

The analysis will involve multiple steps and draw on statistical methods ranging from simple descriptive statistics to the modeling of repeated measures outcome data accounting for potential missing observations. The major outcomes of the study, the BAT mass, circulating batokines, muscle mass, strength, power and quality, and VO₂max will be compared using an unpaired student t-test to explore baseline differences between older athletes and older sedentary groups. Additionally, repeated measures ANOVA will be performed on the dependent variables as a function of the exercise intervention in the older sedentary group. Multiple linear regression will be used to determine how BAT mass and circulating batokines explain variation in physical characteristics of muscle (strength, quality) and cardiovascular health (VO₂max). Sex will be explored as a biological variable.

Potential Risks and Benefits

Potential Benefits

Participants will likely receive no direct benefit from taking part in this research study.

Potential Risks

RMR/RQ. There is no physical risk associated with RMR/RQ. Other risks include a feeling of claustrophobia experienced by some participants while under the transparent “hood”.

Protection Against Risk:

- A member of the study staff will remain with the subject at all times to ensure his/her comfort.

Blood draws and Intravenous lines (lab samples and infusions, e.g.). There is a risk of pain, vasovagal syncope, hematomas, and/or infection at the blood draw site (low risk of serious AEs). The total volume of blood drawn is over the course of the study is approximately 372 mls.

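### The baseline comparison of older athletes with older sedentary adults is unadjusted in non-randomised, unmatched groups aged 65 to 90, so an age gap or systematic sex imbalance could create or hide a difference

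*Combined protocol and SAP*

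**What the plan says.** **Comparison.** The Statistical Analysis Plan lists BAT mass, batokines, muscle mass, strength, power and quality, and VO2max as the major outcomes. They "will be compared using an unpaired student t-test to explore baseline differences between older athletes and older sedentary groups". No covariate is named, and no other test between the older athlete (OA) and older sedentary (OS) groups appears.

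**Groups.** The Randomization section is answered N/A. Group-specific inclusion criteria 9 and 10 define OA and OS by existing exercise habit; OS is set by the weekly amount "of structured exercise and determined by self-report and triaxial accelerometry". Both groups share the criterion "Males and Females between the ages of 65 to 90 years of age" and the same BMI ceiling of 35. Matching or stratification by age or sex is not mentioned.

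**Age.** The Introduction says: "Increased age is also associated with a reduction on physical activity levels and exercise intolerance", and the same sentence carries this through to lower VO2max. The Background says "BAT mass and activity are decreased in humans and mice with aging" and that "12,13-diHOME is decreased in older adults in comparison to young counterparts".

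**Sex.** Under recruitment: "Approximately equal numbers of men and women will be recruited". This is not stated to hold within each group. The analysis plan adds that sex will be explored, without naming a model or term.

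**Regression.** Multiple linear regression will relate BAT mass and batokines to muscle characteristics and VO2max. The plan does not say whether OA and OS are pooled, and it lists no covariates or group term.

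**The concern.** Sample Size Determination gives the primary purpose as understanding the role of physical activity on BAT mass and batokines. The OA-OS contrast is the only between-group evidence for that purpose.

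Age sits on both sides of the contrast. By the protocol's own account it goes with activity, which defines the groups, and with the outcomes. If the OS participants are older on average, an unadjusted t-test credits their age-related lower BAT to inactivity. If the age gap works against the true difference, that difference is hidden. A systematic sex imbalance would act in the same way on any outcome that differs by sex.

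The regressions carry a related but conditional risk. If the two groups are pooled without a group term, and they differ in both BAT and VO2max, the pooled data can show an association that exists in neither group.

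**Working it through.** **Inputs from the documents.** 15 completers per group; unpaired t-test; no randomisation; ages 65 to 90.

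**Assumptions (not in the documents).** Two-sided 5%; within-group outcome SD of 1; age gap of 0.25 to 1 within-group SD (1.5 to 6 years if the age SD is 6); age-outcome correlation *r* of 0.2 to 0.5 in size within each group.

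**The plan's own figure.** There is none to reproduce, because the protocol states that no formal sample size calculation was done. Solving backwards, a t-test with 15 per group has 80% power at a difference of 1.06 SD. That value is used below as a yardstick only.

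**1. Age gap, no true group difference.** Shift in the unadjusted difference = gap × *r*. Noncentrality = shift / √(2/15) = shift / 0.365, on 28 degrees of freedom.

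| Gap (SD) | *r* | Shift (SD) | Noncentrality | t-test rejects | With age and sex |
|---|---|---|---|---|---|
| 0.25 | 0.2 | 0.05 | 0.14 | 5% | about 5% |
| 0.5 | 0.2 | 0.10 | 0.27 | 6% | about 5% |
| 0.5 | 0.5 | 0.25 | 0.68 | 10% | about 5% |
| 1 | 0.2 | 0.20 | 0.55 | 8% | about 5% |
| 1 | 0.5 | 0.50 | 1.37 | 26% | about 5% |

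The t-test column is exact (noncentral t) and agrees with simulation to within about one percentage point. The last column is from simulation.

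**2. Age gap opposing a true difference of 1.06 SD.**

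- Gap 1, *r* 0.5: the unadjusted estimate averages 1.06 − 0.50 = 0.56 SD. Power is about 31% unadjusted against about 78% adjusted.
- Gap 1, *r* 0.2: the estimate averages 1.06 − 0.20 = 0.86 SD. Power is 62% against 69%.
- Gap 0.25, *r* 0.2: the estimate averages 1.06 − 0.05 = 1.01 SD. Power is 76% against 78%.

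**3. Sex.** If sex is unrelated to group, the t-test has no average bias and keeps its 5% level. Overall balance does not ensure balance by group: 10 men of 15 in one group and 5 of 15 in the other still gives 15 men and 15 women. The starting-weight rule for knee-extension 1-RM (90% of body weight for men, 60% for women) shows how this could carry over to strength: (10/15 − 5/15) × 30 = 10 points of body weight with no training effect. That rule sets test loads; it is not outcome data.

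**4. Regression, only if the groups are pooled.** With no within-group association, the pooled correlation is (V × B / 4) / √[(1 + V²/4)(1 + B²/4)], where V and B are the group gaps in VO2max and BAT in SD units.

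- V = 1, B = 0.5: correlation 0.11; false positives 9%.
- V = 2, B = 1.06: correlation 0.33; false positives 46%.

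Age and sex without a group term leave 9% to 43%. A group term restores about 5%. If BAT does not differ between the groups, there is no inflation.

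**The case against.** - **The test is labelled exploratory.** This is fair, and the fix keeps that status. It does not remove the problem, because these are the major outcomes and no other OA-OS analysis is named.
- **The age link is extrapolated.** The activity statement concerns ageing in general, the 12,13-diHOME statement compares older with young adults, and the BAT statement gives no slope within 65 to 90. Both groups also pass the same health screen. All of this stands, so the size is a range, and its low end is negligible.
- **Sex is partly handled.** Recruitment aims for about equal numbers of men and women, and sex will be explored. Nothing in the documents predicts a systematic imbalance. A reader might infer that leaving sex out biases the t-test in any case; it does not.
- **The trial has other evidence.** The OS pre/post training analysis also serves the stated purpose. It compares participants with themselves, so an OA-OS age gap cannot confound it.
- **The regressions may already be sound.** The plan does not say that the groups are pooled, and multiple regression does not exclude a group term. A reader might infer that the regressions are invalid, but the documents show only that they are under-specified. A group term also changes the question if BAT is seen as a mediator of the group difference.
- **Adiposity.** The Background says "There is also an inverse relationship of BAT to body mass index and visceral fat mass", and a reader might infer that adiposity adjustment is also required. Training may itself cause leanness, so a difference that runs through adiposity is not necessarily bias. No such adjustment is asked for here.

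**Conclusion.** The point holds for the OA-OS comparison. The groups are neither randomised nor matched, the protocol itself makes age a plausible confounder, and the only stated between-group test ignores it. Under the assumed ranges the false-positive rate runs from about 5% to 26%, and is 6% to 10% at a 0.5 SD gap. The worst figure needs both a 1 SD gap and a correlation of 0.5. Where the gap opposes a 1.06 SD difference, the loss of power runs from slight to severe (31% against about 78%).

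The documents do not show that the groups will differ in age, or that the comparison will be wrong. They show that the plan has no protection if the groups do differ. The sex part is limited to an actual imbalance between groups, and the regression part to pooled analysis without a group term. This should be fixed. Confidence is medium, because every quantity behind the size is assumed.

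**What to change.** In the Statistical Analysis Plan, replace the t-test sentence with wording such as: *For each major outcome, the baseline OA-OS difference will be estimated with a 95% confidence interval from a linear model with group, age (linear) and sex. This comparison is exploratory. The unadjusted difference will be reported descriptively.*

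For the BAT and batokine regressions, state whether OA and OS are pooled and which association is meant. If they are pooled, include a group term for any claim about an association within groups.

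**Cost.** Only the wording changes: no new visits or measurements are needed, and there is still one model per outcome. The model uses 2 of 28 degrees of freedom. At a 1.06 SD difference:

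- power falls from 80% to about 77% if age and sex are balanced and unrelated to the outcome;
- power falls to about 67% with a 1 SD age gap and no age effect;
- power rises to about 87% with no gap and an age-outcome correlation of 0.5.

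Adjustment does not remove unmeasured confounding, so the report should still describe the contrast as observational.
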